7.1.1. Monitoring and Discontinuation for Suspected Drug-induced Liver Injury (DILI)

Liver chemistry will be evaluated as specified in the SoA (Section [1.3](#)).

Per FDA recommendations, the following criteria for elevations in liver transaminases or bilirubin will be used for closely monitoring, discontinuing, or temporarily interrupting IP.

Definition of baseline ALT and AST values

Baseline value is defined as an average of ALT and AST values performed during Screening and the Baseline (Day 1) visit, as follows:

ALT/AST Screening Assessments			Day 1 ALT/AST Assessment	Baseline Value
Assessment 1	Assessment 2	Assessment 3 (if applicable)		
Normal	Normal	Not applicable	Any	Average of Assessment 1, Assessment 2 and Day 1 (3 tests)
Normal	Abnormal and ≤40% increase from Assessment 1	Not applicable	Any	Average of Assessment 1, Assessment 2 and Day 1 (3 tests)
Normal	Abnormal and >40% increase from Assessment 1	Normal or ≤40% increase from Assessment 1	Any	Average of Assessment 1, Assessment 2, Assessment 3 and Day 1 (4 tests)
		Abnormal and >40% increase from Assessment 1	Not applicable, subject excluded	Not applicable, subject excluded
Abnormal	≤40% increase from Assessment 1	Not applicable	Any	Average of Assessment 1, Assessment 2 and Day 1 (3 tests)

ALT/AST Screening Assessments			Day 1 ALT/AST Assessment	Baseline Value
Assessment 1	Assessment 2	Assessment 3 (if applicable)		
Abnormal	>40% increase from Assessment 1	≤40% increase from Assessment 1	Any	Average of Assessment 1, Assessment 2, Assessment 3 and Day 1 (4 tests)
		>40% increase from Assessment 1	Not applicable, subject excluded	Not applicable, subject excluded

Abbreviations: ALT, alanine aminotransferase; AST, aspartate aminotransferase

New transaminase elevations in subjects with baseline value within the normal range:

For new elevations in transaminases to greater than 2x ULN, repeat measurement should be performed within 48-72 hours¹⁰ of receipt of laboratory results. If elevations persist, subjects should be evaluated for other causes of transaminase elevations and with tests of hepatic function. If no other cause is identified, then the subjects need to be monitored closely (see below), and discontinuation of the IP should be considered.

IP should be discontinued, and the subject followed until resolution of symptoms or signs in the following situations:

- ALT or AST >8x ULN
- ALT or AST >5x ULN for more than 2 weeks
- ALT or AST >3x ULN and (TB¹¹ >2x ULN or INR >1.50¹²)
- ALT or AST >3x ULN with the appearance of fatigue, nausea, vomiting, right upper quadrant pain or tenderness, fever, rash, jaundice (not attributable to Gilbert's syndrome), and/or eosinophilia (>5.0%)

New transaminase elevations in subjects with baseline ALT or AST > ULN

For new elevations in transaminases to greater than 2x baseline value or total bilirubin >1.5x ULN, repeat measurement should be performed within 48-72 hours¹¹ of receipt of laboratory results. If elevations persist, subjects should be evaluated for other causes of transaminase elevations and with tests of hepatic function. If no other cause is identified, then the subjects need to be monitored closely (see below), and discontinuation of the IP should be considered.

IP should be discontinued, and the subject followed until resolution of symptoms or signs in the following situations:

¹⁰ In cases of isolated AST elevation to the indicated threshold, with a clear non-hepatic source for AST elevation (e.g., evidence of significant concurrent creatine phosphokinase elevation), decision regarding need to proceed with DILI work-up will be based on Investigator judgement.

¹¹ In subjects with Gilbert's syndrome, Direct bilirubin >2 x ULN.

¹² Subjects on anti-coagulation therapy must be assessed individually, as INR criterion will not apply.

Table 3: Discontinuation Criteria in Subjects with Abnormal Baseline ALT or AST Values

Baseline Value of ALT/AST	Criteria to Discontinue IP
<2× upper limit of normal (ULN)	if ALT or AST increases to >5× baseline value
≥2× ULN but <5× ULN	if ALT or AST increases to >3× baseline value
≥5× ULN	if ALT or AST increases to >2× baseline value
Other	
if ALT or AST increase to >2× baseline value AND the increase is accompanied by a concomitant total bilirubin increase to >2× ULN OR the INR concomitantly increases by >0.2.
 
if ALT or AST increase to >2× baseline value in the presence of signs and symptom(s) such as fatigue, nausea, vomiting, right upper quadrant pain or tenderness, fever, rash, jaundice (not attributable to Gilbert's syndrome) and/or eosinophil (>5%)

Abbreviations: ALT, alanine aminotransferase; AST, aspartate aminotransferase; INR, normalized ratio; ULN, upper limit of normal

Close Monitoring for Suspected DILI:

- Repeating liver enzymes, serum bilirubin, hematology panel (for eosinophil count), and INR tests two or three times weekly. Frequency of repeat testing can decrease to once a week or less if abnormalities stabilize or the IP has been discontinued and the subject is asymptomatic.
- Obtaining a more detailed history of symptoms and prior or concurrent diseases.
- Obtaining a history of concomitant drug use (including nonprescription medications and herbal and dietary supplement preparations), alcohol use, recreational drug use, and special diets.
- Ruling out acute viral hepatitis types A, B, C, D, and E; autoimmune or alcoholic hepatitis; hypoxic/ischemic hepatopathy; and biliary tract disease.
- Obtaining a history of exposure to environmental chemical agents.
- Obtaining additional tests to evaluate liver function, as appropriate (e.g., INR, direct bilirubin).
- Considering gastroenterology or hepatology consultations.

Note: If a visit to the clinic is not feasible, laboratory testing can be performed by home health and sent to the central laboratory, or locally and the results should be promptly communicated to the Investigator site.

7.1.2. Monitoring and Study Continuation of Subjects with NASH Fibrosis Stage F1 or F4

The initial protocol allowed subjects to be included based on the biopsy read by one of the 2 expert pathologists. Version 3 Amendment #2 (March 11, 2022) changed the biopsy reading methodology to a central panel of 3 independent pathologists. This change in methodology

resulted in a change in fibrosis stage at baseline for some subjects (from F2 or F3 to either F1 or F4). These subjects and subjects evaluated as F4 during the study will be managed as follows:

1. Subjects with baseline fibrosis stage F1 as determined by a consensus of 3 central pathologists may continue all phases of the study and will be analyzed separately as an exploratory population.
2. Subjects with baseline fibrosis stage F4 (cirrhotic) as determined by a consensus panel of 3 central pathologists (as described above) will participate in all phases of the study as an exploratory population and will be analyzed separately provided:
 - a. Their liver disease is considered well compensated as assessed by Child-Pugh Class A criteria (See Section 10.8), and
 - b. There is no evidence of hepatic decompensation (i.e., hepatic encephalopathy, ascites, or bleeding varices) as assessed by the PI according to usual standard of care, and
 - c. There is no evidence of hepatocellular carcinoma as assessed by local standard of care (e.g., ultrasound, CT scan, or MRI imaging methods and/or central AFP measurement). Central AFP measurement will be performed at every scheduled visit and may be done locally if applicable.
 - d. Their MELD Na⁺ score is ≤ 12 . The MELD Na⁺ score can be calculated by the Investigator, if applicable.
3. Subjects who complete the Main Study and have Week 24 biopsy results evaluated as F4 (cirrhotic) will complete all remaining study periods, provided they continue to meet the criteria in 2a-d above.
4. Consistent with these requirements, subjects who are F4 (cirrhotic) and have evidence of decompensation at any time during the study will be discontinued per Section 7.1 discontinuation criteria above.

7.1.3. Pregnancy

A female subject must permanently discontinue IP if she becomes pregnant. See Section 10.4 and Section 8.3.5 for additional details. If a male subject's partner becomes pregnant, the male subject must agree to use condoms with spermicide to prevent potential fetal exposure.

See the SoA (Section 1.3) for data to be collected at the time of IP discontinuation (ET visit).

7.2. Lost to Follow-up

A subject will be considered lost to follow-up if he or she repeatedly fails to return for scheduled visits and is unable to be contacted by the study site.

The following actions must be taken if a subject fails to return to the clinic for a required study visit:

- The site must attempt to contact the subject and reschedule the missed visit/procedures as soon as possible and counsel the subject on the importance of maintaining the assigned visit schedule and ascertain whether or not the subject wishes to or should continue in the study.

- Before a subject is deemed lost to follow-up, the Investigator or designee must make every effort to regain contact with the subject (where possible, 3 telephone calls and, if necessary, a certified letter to the subject's last known mailing address or local equivalent methods). These contact attempts should be documented in the subject's medical record.
- Should the subject continue to be unreachable, he or she will be considered to have withdrawn from the study (and be labelled as lost to follow-up).
- Discontinuation of specific sites or of the study as a whole are handled as part of Appendix 1 (Section 10.1.8).

8. STUDY ASSESSMENTS AND PROCEDURES

- Study procedures and their timing are summarized in the SoA (Section 1.3).
- If multiple assessments are scheduled at the same timepoint, it is recommended that procedures be performed in the following sequence: PROs, 12-lead ECGs, vital signs, physical examination, sample collection for laboratory and PD biomarker tests, and sample collection for PK.
- The Medical Monitor (or designee) should be notified about immediate safety concerns upon occurrence or awareness, as soon as possible. Decisions if the subject should continue or discontinue IP will be per Investigator's discretion, in consultation with the Medical Monitor (or designee), if possible.
- Adherence to the study design requirements, including those specified in the SoA, is essential and required for study conduct.
- Any situation at the site level with potential impact on subject safety or study conduct, including situations related to COVID-19 infection or control measures (Appendix 6, Section 10.6), should be discussed with the Sponsor immediately upon occurrence or awareness to determine potential impact on study subject/s or study conduct.
- All screening evaluations must be completed and reviewed to confirm that potential subjects meet all eligibility criteria. The Investigator will maintain a screening log to record details of all subjects screened and to confirm eligibility or record reasons for screening failure, as applicable.
- Procedures conducted as part of the subject's routine clinical management (e.g., blood count) and obtained before signing of the ICF may be utilized for screening or baseline purposes provided the procedures met the protocol-specified criteria and were performed within the timeframe defined in the SoA.

8.1. Efficacy Assessments

Laboratory-associated PD and biomarker assessments are described in Section 8.5.

8.1.1. Liver Biopsy and Scoring

Liver biopsy remains the gold standard for diagnosing NASH as well as for establishing the degree of liver fibrosis as it can reliably assess the various histopathological patterns characteristic of NASH (Andronescu, 2018; Arab, 2018; Bedossa, 2018; Gunn, 2018). In addition, histopathology scores are used to assess extent of fibrosis before and after treatment. The fibrosis stage ranges from F0 (without fibrosis) to F4 (cirrhosis) per NASH CRN system. Currently, liver biopsy is required by regulatory authorities as a surrogate endpoint to assess drug efficacy in Phase 3 clinical studies.

Paired liver-biopsy will be performed percutaneously (preferred method) per institution standard, at Screening (a recent biopsy within 6 months prior to screening will be acceptable if available for central read evaluation in lieu of screening biopsy) and Week 24 (window of -7 days to +14 days) (as specified in the SoA, Section 1.3). If biopsy is not performed by Week 26 for subjects in QW dose groups, further doses should be held until discussion with Sponsor. Subjects who

permanently discontinue IP at or after Week 16 and before Week 24 of the Main study will also be requested to provide a liver biopsy at ET visit. For any other scenarios of IP discontinuation or withdrawal from the study, consult the Medical Monitor (or designee) regarding biopsy collection.

Biopsy assessment for eligibility and endpoints will be based on NASH CRN. The NASH CRN adopted the system validated by Kleiner et al. (Kleiner, 2005). The NASH CRN semi-quantitative scoring of histological features (steatosis, ballooning degeneration, and lobular inflammation) which together comprise the unweighted sum to produce the NAFLD Activity Score (NAS) and the NASH CRN Fibrosis staging system are as follows:

	Steatosis	Ballooning	Lobular Inflammation
Grade 0	$\leq 5\%$	None	No foci
Grade 1	$>5\%$ and $\leq 33\%$	Few balloon cells	<2 foci/200x
Grade 2	$>33\%$ and $\leq 66\%$	Many cells/prominent ballooning	2-4 foci/200x
Grade 3	$>66\%$		>4 foci/200x

NASH CRN Fibrosis Staging System

Stage	Fibrosis
Stage 0	None
Stage 1	Perisinusoidal or periportal
Stage 1A	Mild, zone 3, perisinusoidal
Stage 1B	Moderate, zone 3, perisinusoidal
Stage 1C	Portal/periportal
Stage 2	Perisinusoidal and portal/periportal
Stage 3	Bridging fibrosis
Stage 4	Cirrhosis

Transjugular or other biopsy methods may be utilized with Medical Monitor (or designee) approval if the Investigator deems it to be a safer option for an individual subject, and if the site has extensive experience with obtaining biopsies of adequate size using the technique. Ideally, liver biopsies should be done after MRI-PDFF.

Details on the biopsy procedure, preparation of slides and central read are provided in the Biopsy Manual. The procedure will be performed by an experienced hepatologist or radiologist. Biopsies will be subject to central read by liver pathologists who are blinded to the treatment group assignment.

In addition to the central read, liver histology will also be quantitatively assessed by an AI-based machine-read analysis.

8.1.2. Magnetic Resonance Imaging – Whole Liver Proton Density Fat Fraction (MRI-PDFF)

MRI-PDFF is a noninvasive, quantitative, and accurate measure of liver fat content (imaging-based biomarker) to assess treatment response in NASH clinical studies (Caussy, 2018). In this study, the MRI-PDFF procedure is used to assess secondary and exploratory endpoints and will be performed at timepoints specified in the SoA.

PDFF

The MRI-PDFF is determined using a 6-echo gradient echo pulse sequence covering the liver in the axial plane. Analysis is performed by semi-automatic contouring of the liver in every slice avoiding major vessels and bile ducts. The method applies multi-peak lipid spectral models and simultaneous quantification and correction for T2. The liver fat value (PDFF) is the pooled median value of all voxels in the identified volume of interest. For more information, refer to the Imaging Manual.

At Screening, MRI-PDFF should ideally be performed prior to the liver biopsy. A historical MRI-PDFF performed within the last 3 months prior to screening may be acceptable if the images are available and evaluable by the central imaging vendor. The proportion of subjects enrolled with MRI-PDFF <8% may be limited at the Sponsor's discretion.

Iron-corrected T1 Mapping (cT1)

Applicable only at sites capable of conducting cT1 imaging.

cT1 imaging is an MRI-derived measurement of iron-corrected T1 mapping (cT1). It is a non-invasive, quantitative and accurate biomarker which correlates with ballooning (Pavlides, 2017; Eddowes, 2018), fibrosis (Banerjee, 2014; Pavlides, 2017; Tunnicliffe, 2017; McDonald, 2018), and NAS (Eddowes, 2018) and has also been shown to predict clinical outcomes (Pavlides, 2016). T1 mapping measures longitudinal relaxation time, which can be used as an indication of regional tissue water content.

cT1 is measured by using the LMS MOLLI sequence, which is a multi-slice, multi-breathhold, cardiac-gated acquisition performed at end-expiration. It is determined using a five-slice transverse acquisition with one breathhold of approximately 10 seconds per slice. This protocol uses a ShMOLLI acquisition on GE and Siemens scanners, and a MOLLI acquisition on Philips.

At Screening, a historical cT1 imaging assessment performed within the last 3 months prior to screening may be acceptable if the images are available and evaluable by the central imaging vendor.

Liver and Spleen Volume

A dedicated axial 3 dimensions (3D) T1-weighted spoiled gradient echo scan with or without fat suppression will be positioned to cover the entire liver and spleen. Analysis will be done using a semiautomated software to delineate the outer borders of the liver and the liver volume will be calculated in liters.

At Screening, a historical liver and spleen volume assessment performed within the last 3 months prior to screening may be acceptable if the images are available and evaluable by the central imaging vendor.

Pancreatic Fat

An IDEAL (iterative decomposition of water and fat with echo asymmetry and least-squares estimation) multi-echo-gradient echo sequence with 6-point gradient echo will be performed in the axial plane centered on the pancreas covering 10 cm of the organ in the feet-head direction. The pancreatic fat will be reported in % of proton density fat fraction.

At Screening assessment, a historical pancreatic fat assessment performed within the last 3 months prior to screening may be acceptable if the images are available and evaluable by the central imaging vendor.

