2.3.2. Benefit Assessment

There are currently no approved products for NASH in the US.

Patients with biopsy-confirmed NASH may derive benefit from treatment with pegozafermin.

In Part 1 of Study BIO89-100-002, repeat administration of ascending doses of pegozafermin (3 mg, 9 mg, 18 mg and 27 mg QW and 18 mg and 36 mg Q2W) for up to 12 weeks in subjects with NASH or PNASH led to robust, significant, and clinically meaningful benefits in key liver parameters observed across all dose groups, with concurrent metabolic benefits. All dose groups

⁴ Phenotypic NASH, defined as at least one of the following: 1) obesity with T2DM. 2) Obesity with evidence of liver injury (either increased alanine aminotransferase [ALT] and/or vibration-controlled transient elastography [VCTE] score ≥ 7 KPa)

demonstrated significant reductions in liver fat (up to 60% reduction compared to baseline; up to 70% reduction compared to placebo), and liver volume (up to 15% reduction) as measured by magnetic resonance imaging-estimated proton density fat fraction (MRI-PDFF). A significant proportion of subjects responded to therapy, with up to 88% and 71% of subjects achieving a $\geq 30\%$ or a $\geq 50\%$ reduction in liver fat versus baseline, respectively. Treatment with pegozafermin also resulted in significant improvements in liver transaminases [up to 44% reduction in alanine aminotransferase (ALT), 38% reduction in aspartate aminotransferase (AST)], and in N-terminal type III collagen propeptide (Pro-C3), a marker of fibrosis (up to 28% reduction) following 12 weeks of treatment. Of note, reduction of liver fat $\geq 30\%$ and ALT decrease ≥ 17 U/L or $\geq 30\%$ have been previously reported to be associated with positive histological outcomes (Harrison, 2020b; Loomba, 2020c). Metabolic benefits of pegozafermin included a favorable effect on lipids, with significant reductions in triglycerides (up to 28% reduction), non-high density lipoprotein (non-HDL) and low density lipoprotein-cholesterol (LDL-c) (up to 16% reduction), and significant increases in the insulin sensitizing hormone adiponectin (up to 61%). All these effects were observed in both dose regimens evaluated (QW and Q2W) and were most prominent at the 27 mg QW dose and the 36 mg Q2W dose. There were no differences between population groups evaluated (biopsy-confirmed NASH or PNASH).

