9.2. Sample Size Determination

The planned sample size is chosen to sufficiently demonstrate the treatment effect in histological response at Week 24 and to enable characterization of the treatment effect size and variability around the histological response to support planning of statistical analyses and powering for the

Phase 3 study and to provide adequate dose response information to support Phase 3 program dose selection.

Approximately 184 subjects will be randomized in a ratio of 16:8:6:24:15 to Placebo QW (N=42), Placebo Q2W (N=22), pegozafermin 15 mg QW (N=16), 30 mg QW (N=64) and 44 mg Q2W (N=40) in each pegozafermin group, respectively.

The sample size is selected based on a placebo response rate of 15% for NASH resolution without worsening of fibrosis and a placebo response rate of 20% for improvement of fibrosis ≥ 1 stage without worsening of NASH. These placebo response rates are supported by a comprehensive review on placebo histological response rates in previously reported NASH studies and recent meta-analyses (Han, 2019; Rinella, 2019; Drenth, 2020; Mesenbrink, 2020; Nikoolenejad, 2020). The anticipated treatment effect is 30% for both histological endpoints, and is supported by the observed pegozafermin effects on both histological endpoints and in reducing MRI-PDFF and ALT in Study BIO89-100-002, the relationship between MRI-PDFF and ALT reduction to histological responses (Hoofnagle, 2013; Seko, 2015; Loomba, 2019; Loomba, 2020a; Loomba, 2020b; Loomba, 2020c), and the observed histological responses in molecules with similar mechanism of action with treatment shorter than or close to 24 weeks (Akero Therapeutics Inc, 2020; Harrison, 2020a; Harrison, 2020b). Hence, the assumed pegozafermin response rates are █% and █% for NASH resolution and fibrosis improvement, respectively. With these assumptions, the sample size of 64 patients per 30mg QW and placebo group will be able to detect the treatment differences with █% power for NASH resolution and █% for fibrosis improvement at a two-sided nominal 0.05 significance level and accounting for a dropout rate of up to █%. For the comparison of the treatment difference between 44mg Q2W group (N=40) and placebo group (N=64), the power will be █% for NASH resolution and █% for fibrosis improvement.

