3.5. Sample Size Considerations

The planned sample size is chosen to sufficiently demonstrate the treatment effect in histological response at Week 24 and to enable characterization of the treatment effect size and variability around the histological response to support planning of statistical analyses and powering for the Phase 3 study and to provide adequate dose response information to support Phase 3 program dose selection.

Approximately 184 subjects will be randomized in a ratio of 16:8:6:24:15 to Placebo QW (N=42), Placebo Q2W (N=22), pegozafermin 15 mg QW (N=16), 30 mg QW (N=64), and 44 mg Q2W (N=40) in each pegozafermin group, respectively.

The sample size is selected based on a placebo response rate of 15% for NASH resolution without worsening of fibrosis and a placebo response rate of 20% for improvement of fibrosis ≥ 1 stage without worsening of NASH. These placebo response rates are supported by a comprehensive review on placebo histological response rates in previously reported NASH studies and recent meta-analyses ([Han, 2019](#) [Rinella, 2019](#); [Drenth, 2020](#); [Mesenbrink, 2020](#); [Nikoolenejad, 2020](#)). The anticipated treatment effect is 30% for both histological endpoints, and is supported by the observed pegozafermin effects on both histological endpoints and in reducing MRI-PDFF and alanine aminotransferase (ALT) in a Phase 1b/2a study BIO89-100-002, the relationship between MRI-PDFF and ALT reduction to histological responses ([Hoofnagle, 2013](#); [Seko, 2015](#); [Loomba, 2019](#); [Loomba, 2020a](#), [Loomba, 2020b](#); [Loomba, 2020c](#)), and the observed histological responses in molecules with similar mechanism of action with treatment shorter than or close to 24 weeks ([Akero Therapeutics Inc, 2020](#); [Harrison, 2020a](#); [Harrison, 2020b](#)). Hence, the assumed pegozafermin response rates are 45% and 50% for NASH resolution and fibrosis improvement, respectively.

With these assumptions, the planned sample size of 64 patients per 30mg QW and placebo group will be able to detect the treatment differences with 94% power for NASH resolution and 92% for fibrosis improvement at a two-sided nominal 0.05 significance level and accounting for a dropout rate of up to 15%. For the comparison of the treatment difference between 44mg Q2W group (N=40) and placebo group (N=64), the power will be 87% for NASH resolution and 83% for fibrosis improvement.

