In addition to the primary analysis, standard sensitivity analyses, namely, sensitivity analyses based on the hypothetical (missingness at random) strategy, return-to-baseline imputation and control-based imputation, will be conducted. The details of these analyses are presented in Table 5. In all cases, a multiple imputation approach will be applied and imputation models will be based on a Bayesian logistic regression model with subject baseline fibrosis stage, diabetes status, age, gender and baseline NAS score included in the model. The estimated effects and associated standard errors from the individual completed data sets will be combined using Rubin's rules to produce a single inferential statement (treatment effect, standard error and p-value).

Table 5: Primary and sensitivity analyses for three types of ICEs

Analysis	ICE-1	ICE-2	ICE-3
Primary analysis	Use all collected outcomes regardless of ICEs. Impute missing outcomes based on an imputation model informed by the relevant baseline data and type of ICE (“none”,1,2,3). If most subjects with ICE have missing outcomes, type of ICE covariate will be removed from the imputation model.		
Sensitivity analysis by ICE type	Set all post-baseline outcomes as missing. Impute missing outcomes based on an imputation model informed by the baseline data alone (return-to-baseline).	Set all outcomes following ICE as missing. Impute missing outcomes based on an imputation model informed by patients who did not have any of the three ICEs using only the data from the placebo arm.	Set all outcomes following ICE as missing. Impute missing outcomes based on an imputation model informed by patients who did not have any of the three ICEs using only the data from the treatment arms.

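### The primary imputation model for a missing Week 24 biopsy leaves out the subject's own on-treatment MRI-PDFF and ALT, which can bias the treatment difference slightly in either direction

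*Protocol*

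**What the plan says.** SAP 7.8.1 sets out multiple imputation for the primary and sensitivity analyses and says that "imputation models will be based on a Bayesian logistic regression model with subject baseline fibrosis stage, diabetes status, age, gender and baseline NAS score" are in the model. The primary row of Table 5 adds ICE type (none, 1, 2 or 3) and removes that term if most subjects with an ICE lack outcomes. SAP 7.8.1.1 imputes within arm, or with arm as a covariate where data are sparse. No post-baseline variable is named.

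The omitted data are collected. SAP 4.1.3 makes change in MRI-PDFF and ALT at Weeks 12 and 24 secondary endpoints, and Protocol 8.1.1 prefers the biopsy to follow the scan. The plan also treats these data as informative about histology:
- Protocol 8.1.2: "MRI-PDFF is a noninvasive, quantitative, and accurate measure of liver fat content (imaging-based biomarker) to assess treatment response in NASH clinical studies". This supports the premise only; it contains no analysis rule.
- Protocol 2.3.2 says that reductions in liver fat and ALT of stated sizes "have been previously reported to be associated with positive histological outcomes".
- Protocol 9.2 uses "the relationship between MRI-PDFF and ALT reduction to histological responses" as part of the support for the 30-point effect on both primary endpoints.

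**The concern.** The plan relies on the link between MRI-PDFF, ALT and histology to size the effect, then ignores it when filling in missing histology. A subject who completes treatment, has a Week 24 scan and ALT, but no second biopsy, is imputed as if those results did not exist. With no ICE, the donors are biopsied subjects in the same arm with similar baseline values.

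Subjects with an ICE may end up in the same position. Protocol 8.1.1 requests an early termination biopsy only after discontinuation from Week 16 to before Week 24, and leaves other cases to consultation with the Medical Monitor. Most subjects with an ICE could therefore lack outcomes, which triggers removal of the ICE term.

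The analysis then assumes that biopsies are missing at random given arm and baseline (and ICE type while it is kept). If missingness also tracks on-treatment response, both arm rates are off and the difference may be too. SAP 3.5 wants this estimate to characterise the effect size and support Phase 3 powering.

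**Working it through.** **1. The plan's own figures.** SAP 3.5 gives "a placebo response rate of 15% for NASH resolution without worsening of fibrosis", a "placebo response rate of 20% for improvement of fibrosis", and says that "the assumed pegozafermin response rates are 45% and 50% for NASH resolution and fibrosis improvement, respectively". Power is "at a two-sided nominal 0.05 significance level and accounting for a dropout rate of up to 15"%. With the two-proportion normal approximation (pooled variance under the null) and n reduced by 15% (64 to 54.4; 40 to 34):
- 30 mg QW v placebo: 93.8% and 91.8% (stated 94% and 92%).
- 44 mg Q2W v placebo: 87.1% and 84.0% (stated 87% and 83%).

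The inputs are therefore understood. The documents give no figure for the effect of the imputation model.

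**2. Effect on one arm.** Ignoring baseline covariates, imputed minus true arm rate = m × (rate in biopsied − true rate in missing), where m is the fraction missing. If 15% are missing on drug and truly respond at the placebo rate, NASH resolution is overstated by 0.15 × (0.45 − 0.15) = 4.5 points. If none of them respond, it is 0.15 × 0.45 = 6.75 points, and 0.15 × 0.50 = 7.5 points for fibrosis improvement. These are errors in one arm's rate. Placebo has an error of the same kind, which partly or wholly cancels in the difference.

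**3. Effect on the difference, NASH resolution.** The documents give neither histological response nor missingness by MRI response, so these are assumptions: MRI response 75% on drug and 25% on placebo; histological response by MRI response 55% v 15% on drug and 36% v 8% on placebo. They return the planned rates: 0.75 × 0.55 + 0.25 × 0.15 = 0.45, and 0.25 × 0.36 + 0.75 × 0.08 = 0.15. MRI non-responders are k times as likely to miss the biopsy.

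*15% missing in each arm, k = 3.* Drug: responders miss 0.15/(0.75 + 0.25 × 3) = 0.10, non-responders 0.30; biopsied rate = (0.75 × 0.90 × 0.55 + 0.25 × 0.70 × 0.15)/0.85 = 0.4676. Placebo: responders miss 0.15/(0.25 + 0.75 × 3) = 0.06, non-responders 0.18; biopsied rate = (0.25 × 0.94 × 0.36 + 0.75 × 0.82 × 0.08)/0.85 = 0.1574. Bias = 0.3102 − 0.30 = +1.0 point.

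*One rule for both arms, 15% overall with equal arms, k = 3.* Responders miss 0.15/(0.5 + 0.5 × 3) = 0.075 and non-responders 0.225, so 11.25% are missing on drug and 18.75% on placebo. Biopsied rates are 0.4627 and 0.1597; bias = +0.3 points. If placebo has the same 40-point gap as drug (45% v 5%, still 0.25 × 0.45 + 0.75 × 0.05 = 0.15), its biopsied rate is 0.1638 and the bias is −0.1 points.

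| k | 15% in each arm | One rule, placebo 36% v 8% | One rule, placebo 45% v 5% |
|---|---|---|---|
| 2 | +0.5 | +0.2 | −0.05 |
| 3 | +1.0 | +0.3 | −0.1 |
| 5 | +1.7 | +0.35 | −0.2 |

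At k = 1 every entry is zero.

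**4. Does using MRI response help?**
- Step 3 inputs, k = 3, 15% missing in each arm, 64 per arm (1500 simulated trials, 30 imputations): the mean difference moves from 0.311 without MRI response to 0.302 with it (true 0.300), and the standard error falls from 0.0831 to 0.0811.
- Harsher inputs (MRI response 80% v 20%; histology 50% v 8% in both arms; 5% of responders and 50% of non-responders missing): the estimate is 0.232 without and 0.252 with MRI response (true 0.251). Here the uncorrected bias is downward, with 0.2 × 0.05 + 0.8 × 0.50 = 41% missing on placebo.
- Missingness of 15% unrelated to response: 0.254 either way.

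**The case against.** A reader might infer that the plan inflates the drug effect, because subjects without liver-fat response are always imputed at the completers' rate. The documents do not support that, for three reasons.

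- **The donor rate is conditional.** Arm is in the model. While the ICE term is kept, SAP 7.8 draws on observed outcomes from similar subjects with the same type of ICE.
- **The sign is open.** Fixing 15% missing in each arm means that, at k = 3, a drug MRI non-responder misses the biopsy 30% of the time and a placebo one 18%, a difference by arm at the same MRI status. Under one common rule the bias shrinks or reverses.
- **The mechanism is indirect.** Protocol 6.4.3 keeps MRI results after Day 1 blinded, so neither subject nor site can act on them. Investigators do review laboratory reports (Protocol 8.2.5), so a route through ALT is possible, but ratios of 3 to 5 have no support in the documents.

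The size is also small: 1.0 point is about 0.12 of a standard error of 8.3 points, and the precision gain is about 2.4% (0.0831 to 0.0811). The 15% is a planning ceiling for dropout, and early dropouts may have no on-treatment scan to use.

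Robustness is partly covered already: a paired-biopsy analysis (SAP 7.8.1), return-to-baseline and control-based imputation (7.8.1.2.1), and missing counted as non-response (7.8.1.2.4). These replace one assumption with another; none uses the subject's own MRI-PDFF or ALT.

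Finally, SAP 7.8.1.1 says that everything collected enters the imputation. Beside a closed list of covariates, and straight after the rules on ICE status, this reads as referring to outcomes collected after an ICE, not as adding predictors.

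All of this limits direction and size. It does not explain leaving out data that the plan itself regards as predictive.

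**Conclusion.** The gap is real and minor. The primary imputation for both primary endpoints omits observed on-treatment predictors. If missing biopsies are related to response, the treatment difference can be biased either way. For NASH resolution the illustrative range is +0.5 to +1.7 points with 15% missing in each arm and −0.2 to +0.35 points under a common missingness rule; it is zero if missingness is unrelated to response. These figures rest on assumed MRI response rates, assumed histological response by MRI status and missingness ratios of 2 to 5. More extreme assumptions give larger values of either sign. No corresponding difference was worked out for fibrosis improvement, though the same model applies. A claim that the plan overstates efficacy would go beyond the evidence.

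**What to change.** In SAP Table 5 (primary row) and 7.8.1.1 Step 1, add percent change in MRI-PDFF and change in ALT as auxiliary predictors for both primary endpoints. Take each from the latest available Main Study visit (Week 24 or early termination, else Week 12). Impute them where missing by fully conditional specification in the same PROC MI step. Use the SAP's own fallback of arm as a covariate where an arm is sparse; 15 mg QW has 16 planned subjects. Reword the sentence in 7.8.1.1 about collected data so that it matches the covariate list.

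The data are already collected, so the cost is SAP wording and two more parameters, settled before unblinding. The downsides are a risk of separation in the smaller arms and little gain for early dropouts with no on-treatment MRI. If the sponsor prefers to leave the primary model alone, the same model as a named sensitivity analysis would be the minimum.
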